- The Nisonger Child Behavior Rating Form teacher version [33]— we will use 30 of the 66 problem items from this rating questionnaire that was adapted for use with children with intellectual disability. Factor analysis of the problem items as rated by teachers led to six sub-scales: conduct problems, insecure/anxious behaviour, hyperactive behaviour, self-injurious/stereotypic behaviour, self-isolated/ritualistic behaviour, and irritable behaviour. We will use three of these sub-scales only as secondary outcomes those in terms of face validity that do not replicate the domains measured by the SDQ: self-injurious/stereotypic behaviour, and irritable behaviour.

6 Study design and setting

Design

A 2-arm cluster feasibility trial of Zippy's Friends (ZF) programme adapted for SEND schools/units, with clear progression criteria and incorporating a process evaluation. Partnership for Children will train and supervise teachers. A sampling frame of potentially eligible schools will be drawn up and the order in which they will be approached will be determined. Following this, these schools will be allocated at random to information sheets describing a study where Usual Practice either does or does not offer delayed access to ZF SEND. Following recruitment, enrolment of pupils, and collection of baseline data, six special schools will be randomised to receive training in ZF SEND and implement it for one academic year; six schools will be randomised to usual practice (UP).

Blinded researchers will assess school-related well-being by interviewing children; teacher and parent-reported data will not be blinded; the statistician will remain blind to allocation prior to analysis. On-line randomisation will utilise minimisation with a random element, balanced by size of school.

What is currently delivered as UP for emotional literacy in SEND schools/units for children with ID will also be established. A survey of 20 SEND schools/units (including the 6 control schools/units) will be conducted to describe UP and a sample of teachers, head teachers and parents will be interviewed for this purpose. Following the completion of data collection, those schools recruited through the route of delayed access to ZF SEND will be offered the programme as delivered by Partnership for Children.

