The nested SWAT will explore the acceptability of two different study designs. One where Usual Practice does not come with the offer of delayed access to ZF SEND, and one where it does. The aim of this SWAT will be to explore the extent to which offer of a 'waitlist' comparator influences recruitment and retention of schools and pupils and modifies what is delivered as Usual Practice during the one-year post-randomisation follow-up period. The findings from this SWAT will be used to inform the design of the subsequent large-scale effectiveness study.

Study setting/context

Twelve SEND schools will be recruited in England (8) and Scotland (4) by the research team. Recruitment will take place directly by contacting SEND schools/units in each Local Authority and through Local Authority and Head Teacher committees and meetings. We will also ask third sector organisations (especially our partner organisations NASEN and BILD) to advise on recruitment strategies. The recruitment methods draw on the successful recruitment routes from the pilot study and also the research team's experience of conducting other research in SEND schools. The intervention will be delivered in schools by the teaching staff.

Recruitment and study duration

It is anticipated that twelve schools will be recruited in the Summer term starting in April 2021 Classes will be identified within those schools and on average 6-10 children and their carers recruited into the study within six weeks of the school electing to take part. Following baseline data collection, those schools allocated to the intervention will deliver it across the 2021/2022 academic year. The study will conclude in 2023.

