9.5 Registration and Randomisation

9.5.1 Randomisation

A sampling frame of potentially eligible schools will be drawn up and the order in which they will be approached will be determined (focussing on geographical areas nearest the study centres). After the order for approaching schools has been determined, schools will be allocated at random to information sheets describing a study where UP either does or does not offer delayed access to ZF SEND and approached consecutively. This randomisation process will be carried out using random permuted blocks. Following recruitment, enrolment of pupils, and baseline data collection, schools will be randomised to ZF SEND or UP using minimisation, with a random element set at 80% to maintain the integrity of the allocation process. Allocations will be balanced on the basis of school size (fewer than 100 pupils total vs 100 or more pupils - informed by special school sized reported by the DfE [35]), and study site (England/Scotland). An online password protected randomisation system will be developed and implemented by staff in the Centre for Trials Research. Randomisation will be carried out by a member of staff who will not be involved in recruitment, data collection, or analysis.

10 Withdrawal & lost to follow-up

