14.1 Randomisation

A sampling frame of potentially eligible schools will be drawn up and the order in which they will be approached will be determined (focussing on geographical areas nearest the study centres). Following this, schools will be allocated at random to information sheets describing a study where UP either does or does not offer delayed access to ZF SEND and approached consecutively. This randomisation process will be carried out using random permuted blocks. Following recruitment, enrolment of pupils, and baseline data collection, schools will be randomised to ZF SEND or UP using minimisation, with a random element set at 80% to maintain the integrity of the allocation process. Allocations will be balanced on the basis of school size (fewer than 100 pupils total vs 100 or more pupils - informed by special school sized reported by the DfE [35]), and study site (England/Scotland). An online password protected randomisation system will be carried out by a member of staff who will not be involved in recruitment, data collection, or analysis.

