14.3 Sample size

We aim to randomise 12 schools (8 in England and 4 in Scotland) in total and six per arm. Based on the pilot study, we estimate there will be one class/group per school and an average of eight children per class (and therefore eight children per school). We will therefore recruit 96 children in total (48 per arm). As this is a feasibility study, we seek to provide estimates of key parameters for a future trial and have not conducted a formal a priori power calculation. If two-thirds (66.7%) of

schools approached agree to take part (i.e. 12 out of 18 approached), the 95% CI around the percentage can be estimated within +/- 21.8% (i.e. 44.9% to 88.5%). Assuming that we obtain 12 month follow-up data for 75% of children, randomising 96 will allow the 95% CI for retention, to be estimated within +/- 8.7%.

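### The school minimisation leaves out SWAT version, so the usual-practice arm may hold too few schools of one version for the SWAT questions that depend on that arm

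*Protocol*

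**What the plan says.** There are two randomisations. Protocol 9.5.1 and 14.1 first allocate schools in the sampling frame, before approach and in permuted blocks, to one of two information sheets: UP with later access to ZF SEND, or UP without it. The second step comes after recruitment, enrolment and baseline: "schools will be randomised to ZF SEND or UP using minimisation, with a random element set at 80% to maintain the integrity of the allocation". The first balancing factor is given as "Allocations will be balanced on the basis of school size (fewer than 100 pupils total vs 100 or more pupils"; the second is added in the words "and study site (England/Scotland"). Section 6 names school size only. SWAT version is a factor in none of these places.

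Section 6 sets the SWAT three targets: recruitment, retention, and whether the waitlist offer "modifies what is delivered as Usual Practice during the one-year post-randomisation follow-up period". Feasibility question 7 in 5.3 repeats the last of these. Section 11.1 recognises no-access and delayed-access sub-groups inside the UP arm.

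On numbers, 14.3 says "We aim to randomise 12 schools (8 in England and 4 in Scotland) in total and six per arm". Section 6 says that "six special schools will be randomised to receive training in ZF SEND and implement it for one academic year" and, for the other arm, that "six schools will be randomised to usual practice (UP"). No rule constraining arm totals is described.

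**The concern.** Whether a waitlist offer changes usual practice can be seen only in schools that end up in UP, and the same holds for retention under UP. That is about six schools, to be split by version. The permuted blocks act on schools before they accept or decline, so they fix neither the mix recruited nor the mix reaching UP, and the second randomisation ignores version. If UP holds one school of a version, or none, there is little or no between-school information on that version, and no later analysis can supply it. The risk grows if one version recruits better, which is one of the effects the SWAT is looking for. Its findings are meant to inform the design of the effectiveness trial.

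**Working it through.** **The plan's own figures.** Six schools × 8 children = 48 per arm, as stated. The two precision figures in 14.3 also reproduce: 1.96 × √(0.667 × 0.333 / 18) = 21.8% and 1.96 × √(0.75 × 0.25 / 96) = 8.7%. None of these bears on the split of versions within UP.

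**Inputs.** From 9.5.1, 14.1 and 14.3: 12 schools, 8 in England and 4 in Scotland; minimisation on size and country; random element 80%, read as probability 0.80 for the arm that reduces imbalance. Assumed, because the protocol does not give them: six small and six large schools, random order of entry, and the split of recruited schools by version.

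**Exact benchmark with UP fixed at six schools.** There are C(12,6) = 924 possible UP arms. The chance that UP holds at most one school of a version is:

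- 6:6 recruited: 2 × (1 + 6 × 6) / 924 = 74/924 = 8.0%
- 7:5: (7 + 5 × 21 + 7) / 924 = 119/924 = 12.9%
- 8:4: (28 + 4 × 56) / 924 = 252/924 = 27.3%
- 9:3: (84 + 3 × 126) / 924 = 462/924 = 50.0%

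**Simulation of the stated minimisation.** Values are rounded; repeat runs differ by up to about one percentage point.

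| Recruited split | At most one of a version in UP, as planned | With version as third factor |
|---|---|---|
| 6:6 | about 10% | about 3% |
| 7:5 | about 15% | about 5% |
| 8:4 | about 28% | about 18% |
| 9:3 | about 50% | about 50% |

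At 9:3 the third factor cannot help much, because three schools shared between two arms leave UP with one about half the time. The chance of none still falls, from about 10% to about 4%.

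**Letting acceptance set the split.** If both versions are accepted by 67% of schools (the 12/18 in 14.3), the risk is about 17% as planned and 6% with the third factor. If acceptance were 50% without access and 80% with delayed access (assumed), it is about 25% and 17%.

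**Other reading of 80%.** If 80% of allocations are deterministic and 20% a coin toss, the favoured arm has probability 0.8 + 0.2 × 0.5 = 0.90. At 6:6 the risk is then 9.3% as planned and 0.3% with the third factor.

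**Arm totals.** At probability 0.80, exactly 6:6 occurs in about 57–60% of allocations, 5:7 or 7:5 in about 37–39%, and a wider gap in 3–4%. Exactly 6:6 rises to about 68% if arm total is an added factor, and to 76–83% at probability 0.90. A 5:7 split raises the standard error of a difference by √[(1/5 + 1/7)/(1/6 + 1/6)] − 1 = 1.4%.

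**The case against.** The case against has real force, and it rules out four stronger readings that a reader might infer.

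- **That the SWAT as a whole is at risk.** Recruitment of schools and pupils by version is settled before the ZF/UP randomisation and is untouched. Only the usual-practice question and retention within UP are exposed. Even there the aim is exploratory and 15.1 makes the analysis descriptive. Section 12.2 has every school describe its usual practice before baseline and at 12 months, so within-school change is available. Perfect balance would give only 3 against 3.
- **That the risk is 28% or 50%.** Those figures need 8:4 or 9:3 splits. The protocol gives one acceptance rate and none by version, so they are scenarios.
- **That the ZF versus UP comparison is confounded with the waitlist offer.** Both steps are random, so any imbalance is by chance. Adding a main effect of version to the outcome model is no clear remedy. It assumes the same shift in both arms, whereas an effect through usual practice would be confined to UP.
- **That the minimisation fails to deliver six per arm.** Section 14.3 words this as an aim, 6:6 is the most likely result, and the usual miss costs almost no precision.

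What remains is that the protocol itself fixes the balancing factors, and they omit the variable that defines the sub-groups one SWAT question compares. An SAP cannot repair that after allocation.

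**Conclusion.** The concern holds as a cheap improvement to the design. Leaving SWAT version out of the minimisation gives about a 10% chance, with evenly recruited versions, that UP holds at most one school of one version, and more if recruitment is uneven. A third factor removes most of that risk at 6:6 and 7:5, about a third of it at 8:4, and at 9:3 only part of the chance of having none. The sizes rest on the 0.80 reading, the assumed size split and the assumed recruited splits; the 6:6 result changes little under the other reading of 80%. The gain is a better chance of a usable descriptive comparison, not a powered one. The mismatch between section 6 and 9.5.1/14.1 on the factors is a plain inconsistency. Six schools per arm is not guaranteed by the stated method, but this is secondary and of little statistical consequence.

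**What to change.** - Add SWAT version (delayed or no access) as a third binary minimisation factor in 9.5.1 and 14.1.
- Bring section 6 into line, since it names school size only.
- State six schools per arm as a target in section 6, as 14.3 already does, and say what the 80% is the probability of.

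The cost is one more field in the randomisation system and slightly looser balance on size and country: mean imbalance rises from about 0.65–0.70 to about 0.75–0.80 schools. The third factor does not secure 6:6; exactly 6:6 stays near 60%.

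If exact arm sizes are wanted, one constrained allocation of all 12 schools would give them. It is an option only if all schools complete baseline together. Section 6 merely anticipates recruitment in one term, 9.3 makes timing depend on COVID-19, and a batch would make every school wait for the last one before the September start.

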10.1 Withdrawal

Participants and their parents have the right to withdraw consent for participation in any aspect of the study at any time. The participants' care will not be affected at any time by declining to participate or withdrawing from the study.

If a participant initially consents but subsequently withdraws from the study, clear distinction must be made as to what aspect of the study the participant is withdrawing from. These aspects could be:

- Withdrawal from intervention
- Partial withdrawal from further data collection (e.g. some questionnaires/ assessments)
- Complete withdrawal from further data collection
- Withdrawal of permission to use data already collected

If consent for video recording is withdrawn or refused then there are three options. Either no researcher recording/observation takes place, or with consent, a researcher could observe the lesson and audio record it or make notes. If consent is withdrawn during the study then we can provide the teacher in question with the choice as to whether we can use any sessions already recorded or for them to be withdrawn from the project.

The withdrawal of participant consent shall not affect the study activities already carried out and the use of data collected prior to participant withdrawal, unless withdrawal is requested by participants. The use of the data collected prior to withdrawal of consent is based on informed consent before its withdrawal.

10.2 Lost to follow up

Members of the research team will keep record of the number of participants lost to follow up and note the reasons for dropping out of the study using a spreadsheet. This will be done by maintaining close liaison between the research team and the schools and the parents. The intervention is part of the general classroom activities. If pupils withdraw from the lesson or are absent for some lessons, the teachers are asked to record reasons why. All outcome measures will continue to be collected so that attendance/non-attendance can be used as a factor in the data analysis.

11 Study Intervention

11.1 Zippy's Friends

Experimental intervention

Zippy's Friends is a manualised, classroom-based programme that aims to develop children's repertoire of coping skills and their ability to adapt those coping skills to various situations. ZF consists of 6 modules: Feelings, Communication, Making and Breaking Relationships, Conflict Resolution, Dealing with Change and Loss, and Coping (see Table 1 for a brief description of the lesson objectives).

Children who are able to think of a larger number of coping skills are better equipped to use them more often in daily situations. Research has confirmed that children generally like to participate in ZF activities that teach them to cope, and that they experience improvements in their quality of life and relationships after participating in these activities [18]. It is important to note that teaching children how to cope does not mean teaching them that one coping strategy is good and another bad. The goal is rather to use a problem solving approach and to teach children to come up with different ways of dealing with social and emotional problems and to self-evaluate. By seeing how characters in the ZF stories cope in different ways, and by experiencing this for themselves in role-plays and other activities, children become better equipped to choose effective strategies. When they successfully handle one difficult situation, they increase their abilities to adapt to future situations, and this can improve their self-esteem, feelings of competence and general well-being.

In mainstream schools, teachers and teaching assistants deliver the programme during routine classroom time over a 24-week period with 45-minute weekly sessions (4 sessions per module). Whilst the mainstream programme is designed for children aged 5-7yrs, our pilot study [5] indicates that the SEND programme caters best for an older age range (9-11). Teachers are advised to take a flexible approach to make the programme 'age appropriate' (including consideration of mental/emotional age).

The ZF SEND programme closely aligns with the mainstream programme but has additional resources and supplements developed by Partnership for Children in consultation with SEND teachers to cater for children with a wide range of abilities. The SEND programme provides a selection of alternative activities (around five for each of the mainstream activities), and the stories have been adapted at four different ability levels using WIDGIT symbols. The activities include craft sessions, completion of worksheets, role-plays, discussion and use of metaphors.

Completion takes longer owing to the increased complexity of running the programme with SEND pupils and to allow for shorter sessions, repetition of sessions and a range of extra activities. SEND teachers deliver two 45-minute sessions a week to cater for this and to ensure adequate time for completion within one academic year. All children in at least one Year 5/6 class in each school will receive the intervention, or will be present and included whenever possible. One aim of the study is to examine the extent of engagement of children with varying levels of ID in the intervention. Parents will be sent materials throughout the programme that can be used in the home to reinforce and generalise the principles of ZF SEND.

Prior to running the programme, teachers attend a 1-day training course organised by Partnership for Children. Teachers will also receive support and supervision through direct observation of one session and attendance at two support meetings. Additional support is available upon request of the teacher who can contact the Partnership for Children mentor at any time for advice and guidance. The programme materials, training and support are provided by Partnership for Children.

At least two teachers (or a teacher and teaching assistant) in each of the six intervention schools will be selected by their senior management to implement the ZF SEND programme. Each school will identify at least one class to take part in the research– either a Year 5 or Year 6 class (or a combined group of Year 5/6 children in smaller schools). The teachers who are trained to deliver the intervention will typically be the class teachers. All training and support will be provided by Partnership for Children.

Module 1 – Feelings	
To improve children's abilities to re	ecognise different emotions and to identify strategies to cope with them.
Session 1	To improve children's abilities to recognise feeling sad and to identify ways to cope.
Feeling sad – feeling happy	
Session 2	To improve children's abilities to recognise feelings of anger and annoyance and to identify ways to cope with
Feeling angry or annoyed	these reelings.
Session 3	To improve children's abilities to identify jealousy and to learn ways to cope with this feeling.
Feeling jealous	
Session 4	To improve children's abilities to recognise feeling nervous and to identify ways to cope with difficult feeling
Feeling nervous	
Module 2 – Communication	
To improve children's abilities to co	ommunicate their feelings and listen to other people.
Session 1	To improve children's abilities to recognise effective and ineffective ways of expressing how they feel.
Improving communication	
Session 2	To improve children's abilities to listen to other people.
Listening	
Session 3	To improve children's abilities to ask for help.
Who can help us?	
Session 4	To improve children's abilities to communicate their feelings and listen to other people.
Saying what we want to say	

Table 1 Lesson objectives for ZF SEND 6 module programme

Module 3 - Making and breaking relationships To improve children's abilities to make friends and to cope with rejection and loneliness. Session 1 To improve children's abilities to keep their friends. How to keep a friend Session 2 To improve children's abilities to cope with loneliness and rejection. Dealing with loneliness and rejection To improve children's abilities to resolve conflicts with their friends. Session 3 How to resolve conflicts with friends Session 4 To improve children's abilities to make friends. How to make friends Module 4 - Conflict Resolution To improve children's abilities to resolve conflicts. Session 1 To increase children's abilities to recognise characteristics of a good solution. How to recognise good solutions Session 2 To improve children's abilities to deal with situations involving bullying. Dealing with bullying Session 3 To improve children's abilities to resolve conflicts, particularly when they are angry. Solving problems Session 4 To improve children's abilities to help others resolve conflicts. Helping others resolve conflicts Module 5 - Dealing with change and loss To improve children's abilities to cope with change and loss. Session 1 To increase children's understanding that change and loss are part of normal everyday experiences. Change and loss are part of life Session 2 To increase children's understanding that death is a normal part of life, and to improve their abilities to cope with situations involving grief and loss. Coping with death Session 3 To improve children's abilities to cope with change and loss. Visit to a graveyard

Session 4	To improve children's understanding that change an loss can have positive effects.
Learning from change and loss	
Module 6 – We cope	
To improve children's abilities to use	e a variety of coping strategies in different situations.
Session 1	To improve children's abilities to use different coping strategies.
Different ways to cope	
Session 2	To improve children's abilities to help others cope with different situations.
How to help others	
Session 3	To improve children's abilities to apply their coping skills to new situations.
Adapting to new situations	
Session 4	To review what we have learned during Zippy's Friends and to celebrate together.
Celebrating together	

Comparator intervention

The comparator intervention will be Usual Practice (UP) - participants will attend their usual classes as well as other services they may be engaged with outside school hours, but without receiving ZF SEND. Because Partnership for Children is the only organisation in the UK offering training in the intervention, there is no possibility of contamination within the control schools during the research. The six schools randomly allocated to the control arm of the study are to receive the same assessment phases as the six intervention schools but will not implement ZF SEND until after 12month follow-up data collection is completed (whether they are in the 'no access' or 'delayed access' sub-group of the UP arm). Records will be kept to monitor group activities and check for potential overlap between UP and ZF SEND contents. UP may include any services (mainstream and specialised) provided to families and their children with ID as a part of an Education Health and Care Plan in England or equivalent in Scotland. We will not include schools/units already delivering a manualised emotional literacy intervention at time of baseline assessments. All other receipt of psychological support or emotional literacy teaching in both arms of the research will be recorded. This will be done using a summary sheet provided for teachers and parents. This will be further explored in qualitative interviews with control arm teachers and parents (see section 8). In addition, services receipt data (see 6.3) collected at baseline and 12 months will be used to fully describe UP.

